5.2 Exclusion criteria

Participants meeting any of the following criteria are not eligible for inclusion in this study.

- 1. Previous treatment (within 90 days of screening) with monoclonal antibodies directed towards PCSK9
- 2. (i) Active liver disease defined as any known current infectious, neoplastic, or metabolic pathology of the liver or (ii) unexplained alanine aminotransferase (ALT), aspartate aminotransferase (AST) elevation >3x ULN, or total bilirubin elevation >2x ULN (except patients with Gilbert's syndrome) at screening confirmed by a repeat measurement at least 1 week apart
- 3. Females who are pregnant or nursing, or who are of child-bearing potential, defined as all women physiologically capable of becoming pregnant (e.g. are menarchal) **unless** they agree to abstinence or, if sexually active, agree to the use of effective methods of contraception during dosing of study treatment. Female participants of child-bearing potential, who are or might become sexually active, must be informed of the need to prevent pregnancy during the study. The effective contraception methods are:
 - Barrier method: Condom or Occlusive cap (e.g. diaphragm or cervical/vault caps). For UK sites only (if applicable): with spermicidal foam/gel/film/cream/ vaginal suppository
 - Use of oral, injected or implanted hormonal methods of contraception or placement of an intrauterine device (IUD) or intrauterine system (IUS) or other forms of hormonal contraception that have comparable efficacy (failure rate <1%), for example hormone vaginal ring or transdermal hormone contraception
 - The decision on the contraceptive method should be reviewed at least every 3 months to evaluate the individual need and compatibility of the method chosen
 - If local regulations deviate from the contraception methods listed above to prevent pregnancy, local regulations apply and will be described in the informed consent form (ICF)
 - Adolescent females who have not reached menarche are exempt from the above requirements; however, to be eligible for inclusion in the study, they must be willing to comply with the above requirements if they gain child-bearing potential during the study
- 4. Any uncontrolled or serious disease, or any medical or surgical condition, that may either interfere with participation in the clinical study, and/or put the participant at significant risk (according to investigator's [or delegate's] judgment) if he/she participates in the clinical study

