6.5.2 Follow-up for toxicities

6.5.2.1 Follow up on potential drug-induced liver injury (DILI) cases

Participants with transaminase increase combined with total bilirubin increase may be indicative of potentially severe DILI, and should be considered as clinically important events and assessed appropriately to establish the diagnosis. The required clinical information, as detailed below, should be sought to obtain the medical diagnosis of the most likely cause of the observed laboratory abnormalities.

The threshold for potential DILI may depend on the participant's baseline AST/ALT and total bilirubin value; participants meeting any of the following criteria will require further follow-up as outlined below:

- For participants with normal ALT and AST and total bilirubin value at baseline: AST or ALT >3.0x ULN combined with total bilirubin >2.0x ULN
- For participants with elevated AST or ALT or total bilirubin value at baseline: [AST or ALT >2.0x baseline] OR [AST or ALT >300 U/L] whichever occurs first combined with [total bilirubin >2.0x baseline AND >2.0x ULN]

As DILI is essentially a diagnosis of exclusion, other causes of abnormal liver tests should be considered and their role clarified before DILI is assumed as the cause of liver injury.

A detailed history, including relevant information such as review of ethanol consumption, concomitant medications, herbal remedies, supplement consumption, history of any preexisting liver conditions or risk factors, should be collected.

Laboratory tests should include ALT, AST, total bilirubin, direct and indirect bilirubin, gammaglutamyl transferase (GGT), glutamate dehydrogenase (GLDH), prothrombin time (PT)/International Normalized Ratio (INR), alkaline phosphatase (ALP), albumin, and creatine (phospho)kinase (C(P)K).

Perform relevant examinations (Ultrasound or Magnetic resonance imaging (MRI), Endoscopic retrograde cholangiopancreatography (ERCP)) as appropriate, to rule out an extrahepatic cause of cholestasis. Cholestasis (is defined as an ALP elevation >2.0x ULN with R value < 2 in participants without bone metastasis, or elevation of the liver-specific ALP isoenzyme in participants with bone metastasis).

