10.2 Additional Safety Monitoring

10.2.1 Liver safety monitoring

To ensure participant safety and enhance reliability in determining the hepatotoxic potential of an investigational drug, a standardized process for identification, monitoring and evaluation of liver events has to be followed.

Please refer to Table 16-3 (Section 16.3 (Appendix 3)) for complete definitions of liver laboratory triggers.

Once a participant is exposed to study treatment, every liver event defined in Table 16-3 should be followed up by the investigator or designated personnel at the trial site, as summarized below. Additional details on actions required in case of liver events are outlined in Table 16-4 and Table 16-5 (Section 16.3 (Appendix 3)). Requirements for follow-up of potential DILI cases is provided in Section 6.5.2.1.

- Repeat liver chemistry tests (i.e. ALT, AST, total bilirubin, direct and indirect bilirubin, PT/INR, ALP, GGT, GLDH, albumin and C(P)K) to confirm elevation.
- These liver chemistry repeats will be performed using the central laboratory. If results will not be available from the central laboratory, then the repeats can also be performed at a local laboratory to monitor the safety of the participant. If a liver event is subsequently reported,

any local liver chemistry tests previously conducted that are associated with this event should have results recorded on an appropriate eCRF.

- If the initial elevation is confirmed, close observation of the participant will be initiated, including consideration of treatment interruption if deemed appropriate.
- Discontinuation of the investigational drug (refer to the Discontinuation of study treatment section), if appropriate
- Hospitalization of the participant, if appropriate
- Causality assessment of the liver event
- Thorough follow-up of the liver event should include
 - These investigations can include based on investigator's discretion: serology tests, imaging and pathology assessments, hepatologist's consultancy; obtaining more detailed history of symptoms and prior or concurrent diseases, history of concomitant drug use, exclusion of underlying liver disease

All follow-up information and procedures performed must be recorded as appropriate in the eCRF.

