16.3 Appendix 3: Liver event and laboratory trigger definitions & follow-up requirements

Table 16-3	Liver event an	d laboratory	trigger	definitions
	Liver event an	u laboratory	uiyyei	ueminuons

Definition/ threshold		
Liver laboratory triggers	• ALT or AST > 5 × ULN	
If ALT, AST and total bilirubin normal at	• ALP > 2 × ULN (in the absence of known bone pathology)	
baseline:	• Total bilirubin > 3 × ULN (in the absence of known Gilbert syndrome)	
	 ALT or AST > 3 × ULN and INR > 1.5 	
	 Potential Hy's Law cases (defined as ALT or AST > 3 × ULN and Total bilirubin > 2 × ULN [mainly conjugated fraction] without notable increase in ALP to > 2 × ULN) 	
	Any clinical event of jaundice (or equivalent term)	
	 ALT or AST > 3 × ULN accompanied by (general) malaise, fatigue, abdominal pain, nausea, or vomiting, or rash with eosinophilia 	
	Any adverse event potentially indicative of a liver toxicity*	
If ALT or AST abnormal at baseline:	• ALT or AST > 2x baseline or > 300 U/L (whichever occurs first)	
*These events cover the following: hepatic failure, fibrosis and cirrhosis, and other liver damage-related conditions; non-infectious hepatitis; benign, malignant and unspecified liver neoplasms. ULN: upper limit of normal		

Table 16-4	Follow up requirements for liver laboratory triggers with liver
	symptoms

Confidential

	ALT or AST	Total bilirubin	Liver Symptoms	Action
ALT or	ALT or AST increase without bilirubin increase:			
	If normal at baseline: ALT or AST > 3 x ULN	Normal For participants	None	 No change to study treatment
	If elevated at baseline: ALT or AST > 2 x baseline or > 300 U/L (whichever occurs first)	with Gilbert's syndrome: No change in baseline total bilirubin		 Measure ALT, AST, ALP, GGT, total bilirubin, direct and indirect bilirubin, PT/INR, albumin, C(P)K, and GLDH in 48-72 hours Follow-up for symptoms
	If normal at baseline: ALT or AST > 5 x ULN for more than two weeks If elevated at baseline: ALT or AST > 3 x baseline or > 300 U/L (whichever occurs first) for more than two weeks	Normal For participants with Gilbert's syndrome: No change in baseline total bilirubin	None	 Interrupt study drug Measure ALT, AST, ALP, GGT, total bilirubin, direct
	If normal at baseline: ALT or AST > 8 x ULN	Normal	None	and indirect bilirubin, PT/INR, albumin, C(P)K,
ALT or	AST increase with bilirubin	increase:		and GLDH in 48-72 hours

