	If normal at baseline: ALT or AST > 3 x ULN If elevated at baseline: ALT or AST > 2 x baseline or > 300 U/L (whichever occurs first)	Total bilirubin > 2 x ULN (or INR > 1.5) For participants with Gilbert's syndrome: Doubling of direct bilirubin	None	 Follow-up for symptoms Initiate close monitoring and workup for competing etiologies Study drug can be restarted only if another etiology is identified and liver enzymes return to
	If normal at baseline: ALT or AST > 3 x ULN If elevated at baseline: ALT or AST > 2 x baseline or > 300 U/L (whichever occurs first)	Normal or elevated	Severe fatigue, nausea, vomiting, right upper quadrant pain	baseline

Criteria	Actions required	Follow-up monitoring		
Total Bilirubin (isolated)				
>1.5 – 3.0 ULN	 Maintain treatment Repeat LFTs within 48-72 hours 	Monitor LFTs weekly until resolutionª to ≤ Grade 1 or to baseline		
> 3 - 10 × ULN (in the absence of known Gilbert syndrome)	 Interrupt treatment Repeat LFT within 48-72 hours Hospitalize if clinically appropriate Establish causality Record the AE and contributing factors (e.g. conmeds, medical history, lab) in the appropriate eCRF(s) 	Monitor LFTs weekly until resolution ^a to ≤ Grade 1 or to baseline (ALT, AST, total bilirubin, albumin, PT/INR, ALP and GGT) Test for hemolysis (e.g. reticulocytes, haptoglobin, unconjugated [indirect] bilirubin)		
> 10 x ULN	 Discontinue the study treatment immediately Hospitalize the participant Establish causality Record the AE and contributing factors(e.g. conmeds, medical history, lab) in the appropriate eCRF(s) 	ALT, AST, total bilirubin, albumin, PT/INR, ALP and GGT until resolution ^a (frequency at investigator discretion)		
Any AE potentially indicative of a liver toxicity	 Consider study treatment interruption or discontinuation Hospitalization if clinically appropriate Establish causality Record the AE and contributing factors(e.g. conmeds, medical history, lab) in the appropriate eCRF(s) 	Investigator discretion		
^a Resolution is defined as an outcome of one of the following: (1) return to baseline values, (2) stable values at three subsequent monitoring visits at least 2 weeks apart, (3) remain at elevated level after a maximum of 6 months, (4) liver transplantation, and (5) death.				

Table 16-5	Follow up requirements for liver laboratory triggers
------------	--

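### Participants with normal ALT/AST but raised bilirubin at baseline are classified inconsistently by the protocol's liver-safety passages, and the conflict runs in both directions

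*Protocol*

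**What the plan says.** **Eligibility (Protocol 5.2, criterion 2).** The bilirubin exclusion reads "total bilirubin elevation >2x ULN (except patients with Gilbert's syndrome"). It concerns unexplained elevations confirmed on repeat. A participant with normal enzymes can therefore enrol with bilirubin between 1x and 2x ULN, or higher with Gilbert's syndrome.

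**Potential DILI (Protocol 6.5.2.1).** There are two branches.
- All three values normal: "For participants with normal ALT and AST and total bilirubin value at baseline: AST or ALT >3.0x ULN combined with total bilirubin >2.0x ULN".
- Any one of the three raised: "For participants with elevated AST or ALT or total bilirubin value at baseline: [AST or ALT >2.0x baseline", or above 300 U/L if that comes first, "combined with [total bilirubin >2.0x baseline AND >2.0x ULN". Both limbs must be met.

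**Liver triggers (Protocol 16.3, Table 16-3).** One row carries the condition "If ALT, AST and total bilirubin normal at" baseline. The other carries "If ALT or AST abnormal at baseline". Section 10.2.1 says that "every liver event defined in Table 16-3 should be followed up by the investigator" or site staff.

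**Actions (Protocol 16.3, Table 16-4).** Rows are split on the ALT/AST baseline only. The combined enzyme-and-bilirubin row starts from "If normal at baseline: ALT or AST > 3 x ULN". It pairs this with total bilirubin above 2x ULN (or INR above 1.5), or with a doubling of direct bilirubin in Gilbert's syndrome. The action is interruption of study drug.

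**Mandatory discontinuation (Protocol 9.1.1).** For unexplained increases, one criterion is ALT or AST above 3x ULN together with bilirubin above 2x ULN or INR above 1.5. It has no baseline split.

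**The concern.** A participant with normal ALT/AST and raised bilirubin is in the elevated-baseline branch of 6.5.2.1, in neither row of Table 16-3, in the normal-baseline rows of Table 16-4, and under an undivided rule in 9.1.1. The same laboratory result can then be a potential DILI case in one passage and not in another, or stop treatment in one passage without counting as potential DILI in another.

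What is at stake is site-level handling of hepatic safety in adolescents: which results start the DILI work-up, which interrupt or end treatment, and which can reach SAE reporting. Two sites following the protocol exactly, but from different passages, could treat the same result differently.

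**Working it through.** The plan states no figure here to reproduce, so the check compares the row conditions and the thresholds.

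**Notation, in multiples of ULN.** Baseline enzyme f, with f ≤ 1 (normal). Baseline total bilirubin b, with b > 1 (raised). Later values are A (ALT or AST) and B (total bilirubin). Assume no Gilbert's syndrome, INR not above 1.5 and no liver symptoms.

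**Rules for this participant.**
- 6.5.2.1: A > 2f and B > max(2b, 2). Because b > 1, the second condition is B > 2b. The 300 U/L alternative would come first only if the baseline enzyme were above 300/2 = 150 U/L.
- Table 16-3: the first row needs b ≤ 1 and the second needs f > 1. Neither holds, so no row applies.
- Table 16-4 combined row, and 9.1.1 if unexplained: A > 3 and B > 2.

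**Enzyme limb.** The 6.5.2.1 limit is 2f, so it is at most 2.0 and always below 3.

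| f | 2f | Table 16-4 |
|---|---|---|
| 0.3 | 0.6 | 3 |
| 0.4 | 0.8 | 3 |
| 0.5 | 1.0 | 3 |
| 1.0 | 2.0 | 3 |

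For f below 0.5 the enzyme limb can be met by a value within the normal range.

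**Bilirubin limb.** This moves the other way. The 6.5.2.1 limit is 2b, always above 2.

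| b | 2b | Table 16-4 |
|---|---|---|
| 1.2 | 2.4 | 2 |
| 1.5 | 3.0 | 2 |
| 2.0 | 4.0 | 2 |

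**Both limbs together.** Since 2f < 3 and 2b > 2 for every such participant, two zones of disagreement always exist:
- 6.5.2.1 only: 2f < A ≤ 3 with B > 2b.
- Table 16-4 only: A > 3 with 2 < B ≤ 2b.

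**Example with f = 0.4 and b = 1.5** (6.5.2.1 limits 0.8 and 3.0):

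| A | B | 6.5.2.1 | Table 16-4 combined row | Table 16-3 |
|---|---|---|---|---|
| 0.9 | 3.1 | met (0.9 > 0.8; 3.1 > 3.0) | not met (0.9 ≤ 3) | no row |
| 3.2 | 2.5 | not met (2.5 ≤ 3.0) | met (3.2 > 3; 2.5 > 2) | no row |
| 3.2 | 3.1 | met | met | no row |

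The second line also meets the 9.1.1 criterion if the rise is unexplained. That result stops treatment but is not a potential DILI case under 6.5.2.1.

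**Gilbert's syndrome.** Table 16-4 replaces the total bilirubin limit with a doubling of direct bilirubin. Section 6.5.2.1 stays with total bilirubin, and the 9.1.1 criterion makes no separate provision.

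**The case against.** The best defence is that these participants are still protected, and much of it stands.

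- **The enzyme limb of 6.5.2.1 never acts alone.** A reader might infer that a normal-range ALT by itself makes a potential DILI case. It does not, because bilirubin must also exceed twice baseline and 2x ULN. Comparing the enzyme limits alone would misstate the discrepancy, since the bilirubin limb differs in the opposite direction.
- **Other provisions apply.** A reader might infer that these participants have no liver trigger at all. That is true of the Table 16-3 row conditions only. The isolated-bilirubin rows of Table 16-5 have no baseline split, and the first example (bilirubin 3.1x ULN) falls in the row for values above 3x up to 10x ULN unless the participant has known Gilbert's syndrome. Table 16-4 and 9.1.1 also apply, and 10.2.1 refers to Tables 16-4 and 16-5 and to 6.5.2.1.
- **SAE reporting is filtered.** Section 6.5.2.1 requires confirmation on repeat testing and no alternative cause, and treats DILI as a diagnosis of exclusion. Many results in this group would not become SAEs.
- **Table 16-3 may have been meant to include Gilbert's syndrome.** Its bilirubin bullet carries a Gilbert exception. That suggests intent but does not change the row condition. The table layout is damaged in the text available, but both row conditions are legible.
- **Summary counts.** A reader might infer that the liver counts seen by the DMC depend on which passage a site follows. This is not shown. SAP Table 5-2 counts by fixed ULN multiples from laboratory data, and the DMC outputs are specified in separate documents.

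None of this makes 6.5.2.1, 9.1.1 and Table 16-4 agree, or gives the group a row in Table 16-3.

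**Conclusion.** The inconsistency is in the text and does not depend on any assumed ULN in U/L. For every participant with normal ALT/AST and raised baseline bilirubin, some results meet 6.5.2.1 but not the Table 16-4 combined row, and others meet the Table 16-4 row (outside Gilbert's syndrome) but not 6.5.2.1. Table 16-3 classifies none of them.

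Its reach is limited. Criterion 2 shows that such participants may enrol, not that any did, and the documents give no count. Each 1% of the 141 enrolled would be 0.01 × 141 = 1.4 participants, and the true number may be zero. The efficacy analyses and the ULN-based liver tables in the SAP are unaffected. What can vary is the work-up, the interruption or discontinuation of study drug, and SAE reporting for individual participants. It is an internal inconsistency worth correcting because it concerns hepatic safety in adolescents, but it does not threaten the trial's conclusions.

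**What to change.** Reconcile 6.5.2.1, 9.1.1, Table 16-3 and Table 16-4, and check the result against Table 16-5. A participant with normal ALT/AST and raised baseline bilirubin, with or without Gilbert's syndrome, should be classified in one consistent way in every passage and should be covered by Table 16-3. The basis of classification and the thresholds are for the sponsor to decide.

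The cost is wording in two sections and two appendix tables. No new test or visit is needed.

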6.6 Additional treatment guidance

6.6.1 Treatment compliance

The investigator must promote compliance by informing the participant that compliance is necessary for the participant's safety and the validity of the study. The investigator should also instruct the participant to adhere closely to the scheduled study visits. Study treatment will not be dispensed to the participant but will be administered at designated study visits at the study site by qualified personnel, facilitating compliance. Study drug dosing information should be captured within each designated visit on an appropriate eCRF. The investigator or designee must also maintain an inventory record of study drug (inclisiran/placebo) received and administered.

6.6.2 Recommended treatment of adverse events

Adverse events should be treated according to local practice and guidelines, and is at the discretion of the investigator and treating physician.

For participants with injection site reaction, antihistamines, local or systemic steroids can be used at the investigator's discretion depending on the severity of the reaction.

Medication used to treat AEs must be recorded on appropriate eCRF page(s).

6.6.3 Emergency breaking of assigned treatment code

Emergency code breaks must only be undertaken when it is required to in order to treat the participant safely. Blinding codes may also be broken after a participant discontinues treatment due to disease progression if deemed essential to allow the investigator to select the participant's next treatment regimen, and after discussion and agreement with the sponsor. Most often, study treatment discontinuation and knowledge of the possible treatment assignments are sufficient to treat a study participant who presents with an emergency condition. Emergency treatment code breaks are performed using the IRT. When the investigator contacts the system to break a treatment code for a participant, he/she must provide the requested participant identifying information and confirm the necessity to break the treatment code for the participant. The investigator will then receive details of the investigational drug treatment for the specified participant and a fax or email confirming this information. The system will automatically inform the Novartis monitor for the site and the study team that the code has been broken.

It is the investigator's responsibility to ensure that there is a dependable procedure in place to allow access to the IRT/code break cards at any time in case of emergency. The investigator will provide:

- protocol number
- name
- participant number

In addition, oral and written information to the participant must be provided on how to contact his/her backup in cases of emergency, or when he/she is unavailable, to ensure that un-blinding can be performed at any time.

Confidential

After an emergency un-blinding, study drug should be permanently discontinued. The participant will continue to be followed up in the study unless informed consent is withdrawn (Section 9.1.1 and Section 9.1.2).

6.7 Preparation and dispensation

Each study site will be supplied with study drug in packaging as described under investigational and control drugs section.

A unique medication number is printed on the study medication label.

Investigator staff will identify the study medication kits to administer to the participant by contacting the IRT and obtaining the medication number(s). The study medication has a 2-part label (base plus tear-off label); immediately before using the medication kit, site personnel will detach the outer part of the label from the packaging and affix it to the source document.

6.7.1 Handling of study treatment and additional treatment

6.7.1.1 Handling of study treatment

Study treatment must be received by a designated person at the study site, handled and stored safely and properly and kept in a secured location to which only the investigator and designated site personnel have access. Upon receipt, all study treatment must be stored according to the instructions specified on the labels.

Clinical supplies are to be dispensed only in accordance with the protocol. Technical complaints are to be reported to the respective Novartis Country Organization Quality Assurance.

Medication labels will be in the local language and comply with the legal requirements of each country. They will include storage conditions for the study treatment but no information about the participant except for the medication number.

The investigator must maintain an accurate record of the shipment and dispensing of study treatment in a drug accountability log. Monitoring of drug accountability will be performed by monitors during site visits or remotely and at the completion of the trial.

At the conclusion of the study, and as appropriate during the course of the study, the investigator will return all unused study treatment, packaging, drug labels, and a copy of the completed drug accountability log to the Novartis monitor or to the Novartis address provided in the investigator folder at each site.

